4.2 RATIONALE FOR STUDY DESIGN

4.2.1 Rationale for Study Population

Patients with nAMD and DME have been selected for inclusion in this study given that these indications are being investigated in the Phase III program (Studies GR40306 and GR40844 in nAMD, and Studies GR40349 and GR40398 in DME). As of May 2022, the

6-mg Faricimab Prefilled Syringe—F. Hoffmann-La Roche Ltd 15/Protocol GR43742, Version 1 faricimab (under the tradename Vabysmo[™]) vial product configuration has been approved in the United States, United Kingdom, Canada, Japan, Thailand, Switzerland, and the United Arab Emirates for the treatment of nAMD and DME by injection into the eye. Licensing applications are currently under health authority review for faricimab in these indications in other countries.

4.2.2 Rationale for Human Factors Observations

The purpose of the usability observations is to observe the use of the PFS configuration in an actual clinical use environment to assess if there are any safety concerns remaining related to the future commercial use of the device components. At the time of the study, the PFS configuration (i.e., its device components) will have gone through full technical development, including design validation to ensure the safety of the PFS and the IFN. However, the PFS configuration will not have received market approval at this time.

4.3 JUSTIFICATION FOR DOSE

The 6-mg dose of faricimab in the PFS has been selected to align with the dose that has been studied in the Phase III program in patients with nAMD (Studies GR40306 and GR40844) and DME (Studies GR40349 and GR40398). The formulation, concentration, and intended injection volume will also remain the same as those used in the Phase III program.

4.4 END OF STUDY DEFINITION

A patient is considered to have completed the study if he or she has completed all phases of the study, including the safety telephone call 7 days after administration of the PFS injection.

The end of this study is defined as the date when approximately 35 patients have received injections, all HCP participants have completed their interviews with the HF observers, and the 7-day (\pm 1 day) reporting period after the PFS injection in the last patient has passed. It is expected that the duration of the investigation (length of study plus enrollment period) will be approximately 1.5 months.

In addition, the Sponsor may decide to terminate the study at any time.

4.5 DURATION OF PARTICIPATION

The total duration of study participation for each patient is expected to be approximately 7 days.

5. STUDY POPULATION

Approximately 35 patients with nAMD or DME will be enrolled in this study.

Prospective approval of protocol deviations to recruitment and enrollment criteria, also known as protocol waivers or exemptions, is not permitted.

5.1 INCLUSION CRITERIA

5.1.1 Inclusion Criteria for Health Care Providers

Criteria necessary for a retina specialist to participate in the clinical in-use study are the following:

- Valid medical license to practice in the United States
- Previous experience performing faricimab IVT injections using the vial and syringe procedure

Note that only the retina specialist or suitably-qualified retina fellows are allowed to perform the injection.

- Ability to pre-screen and recruit patients with nAMD or DME indicated for faricimab IVT therapy within a reasonable time frame (≤30 days)
- Ability to schedule the required baseline examinations and faricimab PFS injection procedures, and undergo clinical in-use evaluation within a relatively short time frame (≤7 days)

All additional HCPs (i.e., retina specialists nurses, assistants, or technicians) involved in the faricimab PFS preparation or injection procedure will be included in the study observations and the post-procedure interviews. All participating retina specialists and additional HCPs will be asked to sign an informed consent form regarding the observations to be conducted before commencing with injection preparation.

5.1.2 Inclusion Criteria for Patients

Patients are eligible to be included in the study only if all of the following criteria apply:

- Signed Informed Consent Form
- Age \geq 18 years at the time of signing Informed Consent Form
- Willing and able to comply with clinic visits and study-related procedures (e.g., video recording during the injection procedure)
- For female patients of childbearing potential: agreement to remain abstinent (refrain from heterosexual intercourse) or use contraception, and agree to refrain from donating eggs, as defined below:

Patients must remain abstinent or use contraceptive methods with a failure rate of < 1% per year during the treatment period and for 3 months after the final dose of faricimab. Patients must refrain from donating eggs during this same period.

A female patient is considered to be of childbearing potential if she is postmenarchal, has not reached a postmenopausal state (\geq 12 continuous months of amenorrhea with no identified cause other than menopause), and is not permanently infertile due to surgery (i.e., removal of ovaries, fallopian tubes, and/or uterus) or another cause as determined by the investigator (e.g., Müllerian agenesis). Per this definition, a woman with a tubal ligation is considered to be of childbearing potential. The definition of childbearing potential may be adapted for alignment with local guidelines or regulations.

Examples of contraceptive methods with a failure rate of <1% per year include bilateral tubal ligation, male sterilization, hormonal contraceptives that inhibit ovulation, hormone-releasing intrauterine devices, and copper intrauterine devices.

The reliability of sexual abstinence should be evaluated in relation to the duration of the clinical trial and the preferred and usual lifestyle of the individual. Periodic abstinence (e.g., calendar, ovulation, symptothermal, or postovulation methods) and withdrawal are not adequate methods of contraception. If required per local guidelines or regulations, locally recognized adequate methods of contraception and information about the reliability of abstinence will be described in the local Informed Consent Form.

- Patients who have a confirmed diagnosis of nAMD (any subtype) or DME in one or both eyes by the study site investigator (only one eye will be selected as the study eye, as determined by the retina specialist) with onset at any time prior to study start
- Patients whose study eye is deemed to be indicated for faricimab IVT treatment at the discretion of the retina specialist
- Patients with historical optical coherence tomography (OCT) data available for the study eye within 30 days prior to Day 1.

5.2 EXCLUSION CRITERIA

5.2.1 Exclusion Criteria for Patients

Patients are excluded from the study if any of the following criteria apply:

• Pregnancy or breastfeeding, or intention to become pregnant during the study or within 3 months after the final dose of faricimab

Female patients of childbearing potential must have a negative urine pregnancy test result during screening and on Day 1.

- Requirement on Day 1 for continuous use of any medications and treatments indicated in Section 6.8.2, Prohibited Therapy
- Participation in an investigational trial that involves treatment with any drug or device (with the exception of vitamins and minerals) within 3 months prior to Day 1
- Stroke (cerebral vascular accident) or myocardial infarction within 6 months prior to Day 1
- History of a severe allergic reaction or anaphylactic reaction to a biologic agent or known hypersensitivity to any component of the faricimab PFS injection, studyrelated procedure preparations, or any of the anesthetic and antimicrobial preparations used by a participant during the study
- History of other disease, metabolic dysfunction, physical examination finding, or clinical laboratory finding giving reasonable suspicion of a condition that

6-mg Faricimab Prefilled Syringe—F. Hoffmann-La Roche Ltd 18/Protocol GR43742, Version 1 contraindicates the use of faricimab or renders the patient at high risk for treatment complications in the opinion of the investigator

- Uncontrolled hypertension (systolic blood pressure >180 mmHg and/or diastolic blood pressure >100 mmHg while a patient is at rest)
- Systemic treatment for suspected or active systemic infection on Day 1
- Patients legally blind in the study eye on Day 1 (legal blindness: Best-corrected visual acuity [BCVA] of 20/200 or less).
- History of or any current clinically relevant intraocular inflammation or ocular inflammatory reaction (any grading from trace and greater is excluded), including non-infectious uveitis or infectious uveitis, or sterile inflammatory reaction after previous IVT injections with any agent in either eye
- Suspected or active ocular or periocular infection in either eye on Day 1
- History of or any current indication of excessive bleeding and recurrent hemorrhages, including any prior excessive intraocular or subconjunctival bleeding or hemorrhages after IVT injection or intraocular procedures in either eye
- Uncontrolled glaucoma in the study eye
- Treatment with any IVT injection in the study eye within the 27 days prior to Day 1
- Any invasive intraocular surgery, prior long-acting therapeutic agent, or ocular drug release device implantation (approved or investigational) in the study eye at any time during the 3 months prior to Day 1
- Treatment with panretinal photocoagulation, laser retinopexy or macular (focal, grid, or micropulse) laser in the study eye within one month prior to Day 1

5.3 LIFESTYLE CONSIDERATIONS

5.3.1 Meals and Dietary Restrictions

This study has no meal or dietary restrictions.

5.3.2 Caffeine, Alcohol, and Tobacco

This study has no caffeine, alcohol, or tobacco restrictions.

5.3.3 Activity

This study has no activity restrictions.

5.3.4 Contraception Requirements

During the study, patients must use contraception or take other precautions as described in Section 5.1.

5.4 SCREEN FAILURES

Individuals who do not meet the criteria for participation in this study (screen failure) cannot be re-screened. The investigator will record reasons for screen failure in the screening log (see Section 8).

6-mg Faricimab Prefilled Syringe—F. Hoffmann-La Roche Ltd 19/Protocol GR43742, Version 1

6. STUDY TREATMENT, OTHER TREATMENTS RELEVANT TO THE STUDY DESIGN, AND CONCOMITANT THERAPY

Study treatment is defined as any investigational treatment, marketed product, placebo, or medical device intended to be administered to a study patient according to the study protocol.

The investigational medicinal product (IMP) for this study is 6-mg faricimab PFS.

6.1 STUDY TREATMENTS ADMINISTERED

Table 3 provides a description of the assigned study treatment for this study.

	Faricimab 6-mg PFS with IFN
Use	Experimental
Drug form	Solution for injection
Unit dose strength(s)	120 mg/mL
Dosage level(s)	6 mg
Formulation(s)	Refer to the Pharmacy manual and/or Investigator's Brochure
Packaging	0.5 mL single-use PFS
Labeling	Per local requirements
Route of administration	IVT injection
Source	Sponsor

Table 3 Study Treatment Description

IFN=injection filter needle; IVT=intravitreal, PFS=prefilled syringe.

Participants will receive a single IVT injection of 0.05 mL of the 120-mg/mL faricimab (6-mg dose) formulation delivered by means of a PFS with a co-packaged IFN at the Day 1 visit by a retina specialist. The retina specialist will conduct post-treatment observation according to standard clinical practice. In addition, all participants will be instructed to immediately contact their retina specialist if their eye becomes red, sensitive to light, painful, or develops a change in vision any time after the injection, including after the reporting period ends.

Any overdose or incorrect administration of study drug will be noted on the Adverse Event electronic Case Report Form (eCRF) as a special situation (see Appendix 2). Any adverse events associated with an overdose or incorrect administration of study drug will also be noted on the Adverse Event reporting form by the Investigator (see Appendix 2).

6.2 PREPARATION, HANDLING, STORAGE, AND ACCOUNTABILITY

The Investigatonal Medicinal Product (IMP) required for completion of this study will be provided by the Sponsor. The study site (i.e., investigator or other authorized personnel [e.g., pharmacist]) is responsible for maintaining records of IMP delivery to the site, IMP inventory at the site, IMP use by each patient, and return of unused IMP, thus enabling reconciliation of all IMP received, and for ensuring that patients are provided with doses specified by the protocol.

The study site should follow all instructions included with each shipment of IMP. The study site will acknowledge receipt of IMP supplied by the Sponsor by returning the appropriate documentation form to confirm the shipment condition and content. Any damaged shipments will be replaced. The investigator or designee must confirm that appropriate temperature conditions have been maintained during transit, either by time monitoring (shipment arrival date and time) or temperature monitoring, for the IMP received and that any discrepancies have been reported and resolved before use of the IMP. The IMP must be stored in a secure, environmentally controlled, and monitored (manual or automated) area in accordance with the labeled storage conditions, with access limited to the investigator and authorized staff.

Only patients enrolled in the study may receive the IMP, and only authorized staff may supply or administer the IMP.

The IMP will be returned to the Sponsor with the appropriate documentation, as per agreement.

Accurate records of the IMP received at, dispensed from, and returned to the Sponsor by the study site should be recorded on the drug accountability log.

Refer to the Instructions for Use and/or the pharmacy manual for information on IMP preparation, storage, handling, and accountability.

Of note, each single-dose PFS will provide a usable amount to deliver a single dose of 6 mg faricimab in a volume of 0.05 mL via IVT injection, using the co-packaged IFN. The PFS and co-packaged IFN utilized in this study are fully representative of the presentation intended for commercialization.

6.3 TREATMENT ASSIGNMENT

This is a non-randomized, open-label study. After eligibility has been established for a patient and written informed consent has been obtained, the study site will obtain the patient's identification number from the Sponsor. All participants will receive 6-mg faricimab with the PFS configuration.

6.4 STUDY TREATMENT COMPLIANCE

When patients are dosed at the site, they will receive study treatment directly from the Investigator or designee, under medical supervision. The date and time of dose administration in the clinic will be recorded in the source documents and on the eCRF. The dose of study treatment and study patient identification will be confirmed at the time of dosing by a member of the study site staff other than the person administering the study treatment.

Details on treatment administration (e.g., dose and timing) should be noted in the source documents and on the Study Drug Administration eCRF. Cases of accidental overdose or medication error, along with any associated adverse events, should be reported as described in Appendix 2.

6.5 DOSE MODIFICATION

Modification of the 6-mg faricimab PFS dose is not permitted.

6.6 CONTINUED ACCESS TO STUDY TREATMENT AFTER THE END OF THE STUDY

The Sponsor will offer continued access to Roche IMP (faricimab in vial form) free of charge to eligible participants in accordance with the Roche Global Policy on Continued Access to Investigational Medicinal Product, as outlined below.

A participant will be eligible to receive Roche IMP (faricimab in vial form) after completing the study if all of the following conditions are met:

- The participant has a sight-threatening or severe medical condition and requires continued Roche IMP treatment for his or her well-being
- There are no appropriate alternative treatments available to the participant
- The participant and his or her doctor comply with and satisfy any legal or regulatory requirements that apply to them

A participant will not be eligible to receive Roche IMP (faricimab in vial form) after completing the study if any of the following conditions are met:

- The Roche IMP is commercially marketed in the participant's country and is reasonably accessible to the participant (e.g., is covered by the participant's insurance or wouldn't otherwise create a financial hardship for the participant) and is reasonably accessible to the participant (e.g., is covered by the participant's insurance or wouldn't otherwise create a financial hardship for the participant's insurance or wouldn't otherwise create a financial hardship for the participant's
- The Sponsor has discontinued development of the IMP or data suggest that the IMP is not effective for nAMD or DME
- The Sponsor has reasonable safety concerns regarding the IMP as a treatment for nAMD or DME

• Provision of the Roche IMP is not permitted under the laws and regulations of the participant's country

The Roche Global Policy on Continued Access to Investigational Medicinal Product is available at the following website:

https://www.roche.com/policy_continued_access_to_investigational_medicines.pdf

6.7 TREATMENT OF OVERDOSE

An overdose is the administration of a drug in a quantity that is higher than the assigned dose. There is no known antidote for treating an overdose. Cases of overdose, along with any associated adverse events, should be reported as described in Appendix 2.

In the event of an overdose, the investigator should take the following steps:

- 1. Contact the Medical Monitor immediately.
- 2. Closely monitor the participant for any adverse event, serious adverse event, or laboratory abnormalities for at least 5 weeks.

Doses higher than the recommended dosing regimen have not been studied. Overdosing with greater than recommended injection volume may increase intraocular pressure (IOP). In the event of an overdose, IOP should be monitored and, if deemed necessary by the treating physician, appropriate treatment should be initiated.

6.8 CONCOMITANT THERAPY

Any medication (e.g., prescription drugs, over-the-counter drugs, vaccines, herbal or homeopathic remedies, nutritional supplements) used by a patient in addition to protocol -mandated treatment from 7 days prior to initiation of study treatment until the conclusion of the patient's study participation must be recorded on the Concomitant Medications eCRF along with the following information:

- Reason for use
- Dates of administration, including start and end dates

The Medical Monitor may be consulted if there are any questions relating to concomitant or prior therapy.

6.8.1 Permitted Therapy

At the discretion of the Investigator, participants may continue to receive medications and standard treatments administered for other conditions, with the exceptions listed in Section 6.8.2.

Of particular note:

• In the event that a patient's fellow eye require treatment for nAMD or DME, treatment is permitted.

- The onset of increased IOP and/or glaucoma in the study eye during a patient's study participation should be treated as clinically indicated.
- The use of topical antimicrobials, anesthesia, and steroids in the study eye and in the fellow eye is permitted at the discretion of the investigator.

6.8.2 Prohibited Therapy

At the discretion of the investigator, patients may continue to receive all medications and standard treatments administered for other conditions. However, after the study drug administration on Day 1 the following medications and treatments are prohibited during study participation:

- Systemic anti-VEGF therapy
- IVT anti-VEGF agents in the study eye
- Planned (non-emergency) ocular or systemic surgical interventions
- Concurrent use of any macular photocoagulation or photodynamic therapy with verteporfin in the study eye
- Other experimental therapies (except those comprising vitamins and minerals)

In addition, the investigator should contact the Medical Monitor if questions arise regarding medications not listed above.

7. DISCONTINUATION OF STUDY TREATMENT AND PATIENT DISCONTINUATION OR WITHDRAWAL

Study and site closure is described in Appendix 1

7.1 DISCONTINUATION OF STUDY TREATMENT

Discontinuation of study treatment is not applicable because each patient will receive only one study treatment administration.

7.2 PATIENT DISCONTINUATION OR WITHDRAWAL FROM THE STUDY

A patient may withdraw from the study at any time at his or her own request or may be withdrawn at any time at the discretion of the investigator for safety, behavioral, compliance, or administrative reasons.

The primary reason for discontinuation from the study should be documented on the appropriate eCRF. If a patient requests to be withdrawn from the study, this request must be documented in the source documents and signed by the investigator.

The patient will be permanently discontinued both from the study treatment and from the study at that time.

If a patient withdraws consent from the study, the Sponsor may retain and continue to use any data collected before withdrawal of consent. Patients who withdraw from the study will be replaced.

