8.3 ADVERSE EVENTS, SERIOUS ADVERSE EVENTS, AND OTHER SAFETY REPORTING

The definitions of adverse event and serious adverse event can be found in Appendix 2.

Adverse events will be reported by the patient (or, when appropriate, by a caregiver, surrogate, or the patient's legally authorized representative).

The investigator and any qualified designees are responsible for detecting, documenting, and recording events that meet the definition of an adverse event or serious adverse event and remain responsible for following up adverse events that are serious, are considered related to the study treatment or study procedures, or caused the patient to discontinue the study (see Section 7).

8.3.1 Time Period and Frequency for Collecting Adverse Event and Serious Adverse Event Information

After informed consent has been obtained but prior to initiation of study drug, only serious adverse events caused by a protocol-mandated intervention should be reported (see Appendix 2). All other medical occurrences deemed significant by the investigator that begin before the start of study treatment but after obtaining informed consent will be recorded on the relevant medical history eCRF, not the Adverse Event eCRF.

All adverse events (ocular and non-ocular) will be reported from the start of treatment until Day 7 after the faricimab PFS injection procedure (see Section 1.3).

All serious adverse events will be recorded and reported to the Sponsor or designee immediately and under no circumstance should this exceed 24 hours, as indicated in Appendix 2. The investigator will submit any updated serious adverse event data to the Sponsor within 24 hours of it being available.

The 7-day reporting period has been determined based on the expected timing of potential procedure-related events. In addition, all patients will be instructed to immediately contact their retina specialist if their eye becomes red, sensitive to light, painful, or develops a change in vision any time after the injection, including after the reporting period ends.

Investigators are not obligated to actively seek adverse event or serious adverse event information after conclusion of study participation. However, if the investigator learns of any serious adverse event, including a death, at any time after a patient has been

6-mg Faricimab Prefilled Syringe—F. Hoffmann-La Roche Ltd 27/Protocol GR43742, Version 1

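### Section 7.2 takes a withdrawn patient off study at once, without saying whether collection of new adverse events to Day 7 continues for a patient already injected

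*Protocol*

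**What the plan says.** Section 7.2 gives two routes out of the study. A patient may ask to leave, or "may be withdrawn at any time at the discretion of the investigator for safety, behavioral, compliance, or administrative reasons". A requirement to document the request follows: "If a patient requests to be withdrawn from the study, this request must be documented in the source documents and signed by the investigator". A separate paragraph then states the consequence: "The patient will be permanently discontinued both from the study treatment and from the study at that time". Withdrawal of consent comes after that, but only as regards use of data already collected, and the section closes with "Patients who withdraw from the study will be replaced".

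Section 7.1 says there is no treatment to stop: "Discontinuation of study treatment is not applicable because each patient will receive only one study treatment administration".

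Section 8.3.1 sets the collection window: "All adverse events (ocular and non-ocular) will be reported from the start of treatment until Day 7 after the faricimab PFS injection procedure". It also says: "Investigators are not obligated to actively seek adverse event or serious adverse event information after conclusion of study participation".

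Appendix 3 (A3-1) has site staff contact all patients at 3 (±1) and 7 (±1) days after the injection to ask about adverse events. Section 8.3 keeps the investigator responsible for events that are serious, that are judged related, or that led the patient to leave. Section 8.3.3 has every reported event followed until it resolves, is stable, or the patient is lost or withdraws consent.

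**The concern.** This is a single-injection study. After Day 1 the patient-level activity still scheduled is the two safety calls, with their adverse event and medication questions. Leaving the study after injection therefore has one main practical consequence, which is whether safety contact goes on. Section 7.2 does not address it. It uses wording suited to a repeated-dose trial, where coming off treatment and coming off study are two different things.

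At stake is the completeness of the 7-day adverse event summary, the only patient-level safety output planned (Sections 3 and 9.3). Section 8.3.1 justifies the 7 days by when procedure-related events are expected. A new event that appears after an early withdrawal but before Day 7 falls within that period, and the site could miss it without breaching Section 7.2.

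**Working it through.** The point turns on the text, so the passages are set against each other first.

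1. **After injection, what can withdrawal end?** Section 7.1 rules out treatment. Table 2 leaves the Day 3 and Day 7 calls.
2. **When does participation end?** Under Section 7.2, at the moment of withdrawal, with no carve-out for an injected patient.
3. **What duty remains to look for new events?** The no-duty sentence in Section 8.3.1 is tied to the end of participation, not to Day 7. Combined with step 2, the duty can lapse on, say, Day 2.
4. **What points the other way?** The Day 7 rule in Section 8.3.1 and the calls to all patients in Appendix 3. Neither has an exception for withdrawn patients. Steps 3 and 4 cannot both govern the same injected, withdrawn patient.
5. **What is already protected?** Events reported before withdrawal. Sections 8.3 and 8.3.3 keep these under follow-up, and withdrawal by the investigator is not among the end points in Section 8.3.3.
6. **What is left?** New events between withdrawal and Day 7 in an injected patient who has not refused contact.

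The arithmetic gives scale only.

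- *The plan's own figure (Section 9.2):* about 12 patients per team × 3 teams = 36, consistent with the stated approximately 35. The stated minimum is 30.
- *One unobserved patient:* 1/35 = 2.9% (1/30 = 3.3% at the minimum).
- *Assumed range:* the protocol gives no withdrawal rate, so take w = 0 to 3 injected patients withdrawn before Day 7. Suppose there are no events among the 35 − w followed. The one-sided 95% upper bound is 1 − 0.05^(1/(35 − w)). The worst case, in which every unfollowed patient has a late event, is w/35.

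| w | followed | upper bound with 0 events | worst case w/35 |
|---|---|---|---|
| 0 | 35 | 8.2% | 0% |
| 1 | 34 | 8.4% | 2.9% |
| 2 | 33 | 8.7% | 5.7% |
| 3 | 32 | 8.9% | 8.6% |

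The loss of precision is trivial. Any effect would come from events not seen. Replacement restores the number of patients but not the missing observation. If one withdrawn patient stays in the summary alongside a replacement, the share is 1/36 = 2.8%.

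**The case against.** There are four good arguments for leaving the text as it is.

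- **Nothing says the calls stop.** That is an inference from two sections, and Appendix 3 says that all patients are called. This stands: the documents show an unreconciled conflict, not a rule ending the calls.
- **The sentence in Section 7.2 may cover only a patient's own request**, because it comes straight after the sentence on such requests. This stands as a possible reading. But it is its own paragraph in a section that opens with both routes. Even on the narrow reading, asking to leave the study is not the same as refusing a safety call.
- **The no-duty sentence is meant for the time after the reporting period**, which A2-6 ends at Day 7. That is probably the intention, but the sentence is worded around participation, which Section 7.2 can end sooner.
- **Patients are told to contact their retina specialist at once about ocular symptoms.** True, and it reduces the risk. It relies on the patient to call, and it does not cover non-ocular events.

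A reader might go further and infer that contact is lost for the patients most likely to have events, so that the 7-day incidence is biased downward and a true 1/35 is reported as 0/35. The documents do not support that. A patient withdrawn for safety would usually already have a recorded event, would already count in the incidence, and stays under follow-up for that event. A shift from 1/35 to 0/35 needs a patient withdrawn with no recorded event, for example for an administrative reason, and there the link between withdrawal and outcome is weakest. Nor does the protocol say that injected patients who are replaced are dropped from the summary.

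**Conclusion.** The point holds as a limited inconsistency. Read literally, Section 7.2 with the no-duty sentence in Section 8.3.1 permits a site to stop looking for new events before Day 7 in an injected patient, contrary to the Day 7 rule in Section 8.3.1 and the calls in Appendix 3. Events already reported are protected.

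The likely effect is small: one injection, a 7-day window, descriptive summaries, no hypothesis test and no patient safety endpoint. The 2.9% per patient is a ceiling for illustration, and the 0 to 3 withdrawals are an assumption. Ending contact is proper when a patient refuses it. The change is still worth making, because the rule as written can lose safety data inside the protocol's own window and costs very little to repair.

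**What to change.** Reconcile Section 7.2 with Sections 7.1, 8.3, 8.3.1, 8.3.3 and Appendix 3:

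- State that, for any injected patient who leaves the study by either route without withdrawing consent to further contact, the calls already planned and adverse event collection continue through Day 7.
- Limit immediate, complete discontinuation to patients not yet injected and to those who refuse further contact.
- Remove the reference to discontinuing study treatment for a patient already injected, since Section 7.1 says it does not apply.
- Tie the no-duty sentence in Section 8.3.1 to the end of the 7-day reporting period.

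The cost is minor wording changes and at most two calls per such patient, both already in the schedule. The consent form is not available here, so check whether its wording on withdrawal needs to match. Sample size and analysis are unchanged.
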